8.8. Drug Accountability

Sponsor will provide the study drug supply. All study drug(s) will be supplied to the Investigator by Sponsor or its designee. Study drug supplies must be kept in an appropriate, secure locked area and stored in accordance with the conditions specified on the labels (approximately -20°C). The Investigator or designated study person must maintain an accurate record of dispensing the study drug in a Drug Accountability Log, a copy of which must be given to Sponsor at the end of the study. The Drug Accountability Log will record the study drugs received, dosages prepared, time prepared, doses dispensed, and doses and/or vials destroyed. The Drug Accountability Log will be reviewed by the field monitor during site visits and at the completion of the study.

8.9. Dose Adjustments

Intrasubject dose reductions for the management of toxicities are not permitted unless discussed with and approved by the Sponsor Medical Monitor.

8.10. Incomplete Dosing

Depending on the technique used for injection, it is possible that a single tumor will not allow for the full volume of administration. Every effort should be made to deliver the total dose, across the permitted number of tumors. Depending on the overall tumor burden this may not be possible, in which case it should be recorded in the CRF. If the tumor shrinks after one or more injections, the total volume declines, less total drug can be given, this will be recorded in the CRF.

8.11. Dose Delay

Delay of up to 14 days are permitted for treating on the next cycle for safety reasons. If the delay is greater than 2 weeks, then the subject should come off study unless discussed with and approved by the medical monitor. These delays are not intended for administrative type/scheduling issues due to holidays, weather, etc. The visit windows in [Table 10](#) should be used in such circumstances. If, in the case of such delay it is beyond the allowed visit window, approval via a Protocol Waiver Form from Sponsor Medical Monitor should be obtained prior to the visit occurring.

8.12. Permanent Discontinuation of Study Drug Due to Adverse Events

INT230-6 should be permanently discontinued for a subject due to the occurrence of any of the following AEs that have not resolved prior to the next treatment

- Any CTC Grade ≥ 3 immunologic related event that persists >1 week despite treatment per institutional guidelines
- CTC Grade 4 neutropenia > 7 days or neutropenic fever
- Persistent \geq CTC Grade 3 anemia despite growth factor support
- Platelets $< 70,000$ for superficial tumors, $< 100,000$ for deep tumors
- \geq CTC Grade 3 elevation in liver enzymes
- \geq CTC Grade 4 neuropathy
- Creatinine > 1.5 mg/dl
- Any anaphylactic type reactions
- \geq Grade 3 nausea or vomiting that persists despite maximal supportive care

- Any AE, laboratory abnormality, or intercurrent illness which, in the judgement of the Investigator, presents a substantial clinical risk to the subject with continued treatment

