5.2.1. E. SUPERFICAL and/or DEEP TUMORS (cohort EC3) Monotherapy of INT230-6

This cohort has simplified the dosing to inject up to the 175mL total dose of INT230-6 into a subject's tumors at each treatment (5 total for induction) session. There is 1 mL of INT230-6 dosed for each 3 cc of tumor volume (1:3) ratio with an induction dosing of 1 doses every 2 weeks for 5 doses with maximum fixed total dose of 175 mL with a maintenance dose of the same maximum of 175 mL given Q9 weeks +/- 10 days. Each tumor should receive up to its

maximum dose to achieve the 1:3 target ratio. The total dose is to be divided up and injected into as many tumors as feasible, with the aim to treat as many visible tumors as possible 1 to 3 times during the course of the induction treatment. After the 5 doses, subjects continue to the maintenance phase where they can repeat injecting new lesions or previously injected lesions with up to 175mL once every 9 weeks. Treatment should continue until patient's tumors disappear (CR), confirmed progression (iCPD) or 2 years whichever is first.

5.2.2. DEC2 Cohorts. COMBINATION WITH ANTI-PD-1 agent(s): see Supplement A for details on each PD-1 agent.

DEC cohorts were initiated and are a combination of INT230-6 plus an anti-PD-1 therapy. The subject population (tumor types) and other details for this group of subjects is defined in Supplement A.

5.2.3. FEC Cohorts. COMBINATION WITH ANTI-CTLA4 agent(s): see Supplement B for protocol details for INT230-6 combinations with anti-CTLA-4 agent(s).

Cohort FEC was initiated and is a combination of INT230-6 plus an anti-CTLA4 therapy. The subject population (tumor types) and other details for this group of subjects is defined in Supplement B.

5.2.4. GEC Cohorts. Cohorts containing the letter “G” dose INT230-6 with agents other than PD-(L)1 or CTLA-4 antibodies.

The subject population (tumor types) and other details for this potential group of subjects will be defined in a future Supplement C.

Study Steering Committee

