9.2.1. Management of select AEs

The following table describes potential AEs and the management suggestions for INT230-6. The investigator should use good medical judgement in determining the optimal care for his or her subjects.

Table 9: Dose Modification and Toxicity Management Guidelines for AEs Associated with INT230-6 using CTCAEv4.03

General instructions:

1. For situations where INT230-6 has been withheld, INT230-6 can be resumed after AE has been reduced to baseline or Grade 1
2. For severe and life-threatening AEs, INT230-6 should be permanently discontinued

AEs	Action taken to INT230-6	AE management	Monitor and follow-up
Allergic reaction or hypersensitivity	Hold drug if Grade ≥ 3	Follow the package insert for CIS and VBL, these AEs usually can be managed with by administration of epinephrine, corticosteroids, and antihistamines.	You may consider a rechallenge with INT230-6 if grade ≤ 2 and resolves with minimal treatment.
Typical cytotoxic effects including fatigue, nausea, vomiting, anorexia, decreased appetite	Hold drug if Grade ≥ 3	Supportive care as per institutional guidelines	Consider using anti-emetic premedication on next INT230-6 dose
Local reactions	Hold drug if Grade ≥ 3	apply heat packs, subcutaneous hyaluronidase	Consider prophylactic antihistamines and low dose corticosteroids on next INT230-6 dose
Injection pain	Hold drug if Grade ≥ 3	Pain control medications as prophylaxis and for treatment as per institutional standard	Consider prophylactic pain medication prior to subsequent injections. If Grade 3 or higher, do not increase INT230-6 dose

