12.1.3. Treatment Period

The Treatment Period of the study is divided into 28 day cycles with associated evaluations and procedures that must be performed at specific time points (see [Table 11](#)) every 28 day dosing and [Table 12](#) every 14 day dosing). Subjects who meet selection criteria may start INT230-6 treatment within 28 days of screening. Subjects will receive injections of INT230-6 every 14 or 28 days based on their Cohort assignment. INT230-6 will also be dosed every 9 weeks +/- 10 days in the cohorts specifying maintenance dosing (EC3, DEC2, FEC and potentially GEC). Results of assessments must be reviewed before administering the next dose. The maximum duration of study therapy to be administered to an individual subject in this study is 2 years (up to maximum of 4 months of initial treatment plus maintenance therapies for certain cohorts as well as Follow up and Survival Follow up).

Every effort should be made to schedule visits within the protocol-specified windows. For injection delays (i.e., by 1 to 13 days) or missed doses, see Section [8.11](#) for administration details. A subject who is withdrawn from the study before the completion of the first cycle for a reason other than a DLT will be replaced.

12.1.3.1. Cycle 1

A cycle is defined as 28 days. Dose 1 (Cycle 1 Day 0) 1 will begin with the first IT injection of INT230-6 (Day 0) and will continue through to completion of evaluations by Day 28. For cohorts A1 and B1 subjects will be dosed every 28 days for a total of 5 cycles (Days 0, 28, 56, 84 and 112) with a response assessment every 2 months for the first year and then every 3 months until progression. In "E" Cohorts, subjects will be dosed every 14 days for a total of 3 cycles (Days 0, 14, 28, 42, and 56).

During Cycle 1 Day 0, the following evaluations will be performed as indicated in [Table 11](#) for 28 day dosing and in [Table 12](#) for 14 day dosing. Results will be recorded on the CRF:

- Physical Exam: A full physical Exam will be performed on Day 0. A Targeted physical examination (including measurement of vital signs as well as pulmonary, heart, abdomen, and skin assessments) will be conducted at all subsequent visits;

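### The lead-in of Section 8.12 ties every permanent-stop trigger for INT230-6 to non-resolution at the next dose, which conflicts with some of its own bullets and with Table 9

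*Protocol*

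**What the plan says.** Section 8.12 lists ten grounds for permanently stopping INT230-6 and introduces them with one condition: the drug is stopped "due to the occurrence of any of the following AEs that have not resolved prior to the next treatment". No bullet is exempted.

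The bullets are of different kinds:

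- Occurrence: "Any anaphylactic type reactions", and the second half of "CTC Grade 4 neutropenia > 7 days or neutropenic fever".
- Printed duration: the first half of "CTC Grade 4 neutropenia > 7 days or neutropenic fever", and a Grade 3 or higher "immunologic related event that persists >1 week despite treatment per institutional guidelines".
- Laboratory values or continuing toxicity: platelets, creatinine, liver enzymes, persistent anemia, neuropathy, and nausea or vomiting that persists.
- Investigator judgement: anything that "presents a substantial clinical risk to the subject with continued treatment".

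Three other places bear on the same decision. Table 9 (Section 9.2.1), general instruction 2, calls for a permanent stop after severe or life-threatening events and sets no resolution condition. General instruction 1 lets a withheld drug resume once the event is back at baseline or Grade 1. The allergic-reaction row says to hold at Grade 3 or above, and its rechallenge remark ("You may consider a rechallenge with INT230-6 if grade") covers Grade 2 or lower only. Section 12.1.6 makes stopping mandatory when the investigator thinks an adverse event makes continuing contrary to the subject's interest.

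**The concern.** A trigger worded as any occurrence and a lead-in that excludes resolved events cannot both be applied to an acute reaction that clears before the next injection. A site that follows the lead-in may re-inject; a site that follows the bullet stops.

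Subject safety is affected first. The data are affected too: the recorded action taken with study drug (Section 13.1), the summaries of withdrawal due to adverse events (Protocol Section 14.3.5, SAP Section 10.1), and the exposure during which later drug-related Grade 3 or higher events can occur. Those events are the primary measure (Section 4.2).

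**Working it through.** The plan gives no figure to reproduce, so the check is mainly logical, with simple day counts.

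**Inputs.** Dosing interval: "Subjects will receive injections of INT230-6 every 14 or 28 days based on their Cohort assignment" (Section 12.1.3). Maintenance: "maintenance dose of the same maximum of 175 mL given Q9 weeks +/- 10 days" (Section 5.2.1), which is 63 - 10 = 53 to 63 + 10 = 73 days. Permitted safety delay: up to 14 days (Section 8.11).

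**Step 1, the rule as written.** Stop under 8.12 = (event meets its bullet) AND (event unresolved before the next treatment).

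**Step 2, occurrence triggers.** The documents give no duration for an anaphylactic-type reaction. I assume hours to days; any duration that ends before the next dose gives the same result. First condition true, second false: no stop under 8.12. Neutropenic fever that clears before the next dose gives the same answer. If it is still present at the next dose, it qualifies.

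**Step 3, duration triggers.** Let onset be day s after a dose and the next dose be day T. In whole days, an event lasting more than 7 days meets its bullet from day s + 8. If it then resolves before day T, it fails the lead-in. The gap runs from day s + 8 to about day T. For s = 0:

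| Schedule | T | Gap | With a 14-day delay |
|---|---|---|---|
| 14-day | 14 | days 8 to 14 | to 14 + 14 = 28 |
| 28-day | 28 | days 8 to 28 | to 28 + 14 = 42 |
| Maintenance | 53-73 | day 8 to about 53-73 | not computed |

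Later onset narrows the gap. On the 14-day schedule, s = 5 leaves days 13 to 14. With s = 7 the start would be day 15, after the next dose, so there is no gap.

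**Step 4, the remaining bullets.** Laboratory values and persisting toxicities can sensibly be checked before redosing, so the lead-in suits them. The investigator-judgement bullet does not rescue the section, because it sits under the same lead-in.

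**Step 5, one event across the protocol.** Take a Grade 3 hypersensitivity reaction of anaphylactic type that has resolved. Grade 3 counts as severe in Sections 13.1 and 14.3.5.

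| Text | Instruction |
|---|---|
| 8.12 with its lead-in | no permanent stop |
| 8.12 bullet alone | stop |
| Table 9, instruction 2 | stop |
| Table 9, allergic row with instruction 1 | hold, may resume; rechallenge remark does not cover Grade 3 |
| 12.1.6 | stop if the investigator so judges |

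**The case against.** The strongest reply is that 8.12 is not the only stopping rule and does not claim to be. Table 9 instruction 2 and Section 12.1.6 can stop the drug after a resolved event, and Section 9.1.1 sends drug-related Grade 3 or higher events after cycle 1 to the steering committee. A reader might infer that a resolved anaphylactic reaction can never lead to a permanent stop. The documents do not support that; it is true inside 8.12 only. The other sections do not make practice uniform, however. Table 9 is introduced as suggestions and points both ways, and 12.1.6 depends on individual judgement.

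A second reply is that requiring an event to be both long-lasting and still present at redosing is coherent. That stands. A reader might infer that the dosing interval overrides the printed limits, but both tests apply. An immune event that begins 5 days before the next dose is unresolved then, yet has not lasted a week, so the printed limit decides.

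Third, any rule tied to the next treatment varies with the interval, and Section 5.5 uses a similar gate (no persistent event above Grade 2). That also stands: dependence on schedule is a consequence to make explicit, not an error in itself.

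Finally, the practical reach may be small. The rationale for Amendment 5 reports one technical DLT among 55 treated patients and mainly low-grade pain. The SAP gives a final enrollment of 110, and its revision log mentions preparing for closure.

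**Conclusion.** The inconsistency is real and sits in a stated stopping rule. Read literally, 8.12 does not stop INT230-6 for occurrence-type events that resolve before the next dose. It also sets aside duration-type events that exceed their printed limit and then resolve in time. Table 9 contradicts it and is itself divided.

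The size is a gap in the rule, not a shift in an estimate: from day 8 to about day 14, 28, or 53-73 by schedule, for onset on the dosing day and before any delay. A reader might turn this into a required persistence 2 to 9 times the printed week (14/7 = 2; 63/7 = 9). Those ratios hold only for dosing-day onset and fall toward just over 7 days as onset moves later. Nor is the whole list void, since the laboratory bullets work as written.

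The documents do not show how many subjects had such an event, so the effect on the primary safety rate cannot be quantified. The INT230-6 discontinuation text for the combination cohorts (Sections 21.3 and 27.3) was not available, so the conclusion covers the main protocol only.

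**What to change.** Reconcile Section 8.12, Table 9 (both general instructions and the allergic-reaction row) and Section 12.1.6. For each event listed in 8.12, state whether it applies on occurrence, after its printed duration, or only if unresolved at the next dose, and say how this works in induction and in maintenance. Check Sections 21.3 and 27.3 of the supplements for the same lead-in. Which clinical rule is right is for the sponsor's clinicians.

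The cost is a wording change and a site notice, with no new data or procedures. If dosing has ended, a notice achieves nothing; the study report should then state which reading the sites applied, so that discontinuation counts and exposure after a listed event can be interpreted.

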8.13. Destruction of Study Drug

If study drugs (those supplied by the sponsor or sourced by the investigator) are to be destroyed on site, it is the investigator's responsibility to ensure the destruction of drug is according to applicable regulations, guidelines and institutional procedures. Appropriate records of the disposal must be maintained at all times. The unused study drugs can only be destroyed after being inspected and reconciled by the responsible Sponsor Study Monitor.

8.14. Return of Study Drug

Study drug will not be returned. All unused and/or partially used study drug may be destroyed on site providing the site has an applicable standard operating procedure on file.

9. TOXICITY AND MANAGEMENT

9.1. Dose Escalation

Cohorts A1, B1, EA, EC, EC2, DEC escalated doses. Cohorts EC3, DEC2, FEC start out with a fixed total dose for each treatment session. For doses within Cohorts EC3, DEC2, FEC, investigators may decide to treat certain tumors on one visit and then treat additional tumors on subsequent visits that may involve an increase of INT230-6 dose given. This section describes the management of the potential toxicities.

9.1.1. Dose-limiting Toxicity

A DLT is defined as a \geq Grade 3 study drug-related adverse event (using NCI CTCAE Version 4.03) occurring during the first dose (DLT window extends up to 28 days after dosing), excluding:

- Grade 3 adverse event of tumor injection reaction (defined as local pain, irritation, or rash localized at sites of known or suspected tumor) that resolves with supportive care measures within 48 hours
- Grade 3 or 4 nausea or vomiting that is adequately treated with supportive care and that resolve within one to two days
- Any bleeding that is self-limiting from or near the site of injection and resolves within 24 hours with non-invasive measures and without the need for transfusion
- Grade 3 or 4 electrolyte abnormalities that correct to below grade 3 with standard measures within 48 hours

A DLT will be considered related to study drug unless there is a clear, well-documented, alternative explanation for the toxicity. Delayed DLTs are adverse events that meet the criteria of DLTs that occur after Cycle 1. If >1 member of a cohort should have a DLT for Doses 2 - 5, then the SSC will determine how accrual shall proceed for that cohort.

Intrasubject dose escalation

Any events of \geq Grade 3 that are considered study drug-related after cycle 1 for a subject will be reviewed by the SSC to assess if alterations in dosing levels and or frequency are needed for that subject. If more than one member of a cohort should have a \geq Grade 3 event for cycles 2 to 5, then the SSC will determine how accrual should proceed for that cohort.

All adverse events that meet DLT criteria must be reported to the pharmacovigilance services vendor (ProPharma) within 24 hours of the study site being made aware of the event using the rapid notification procedures described in Section 13.3.2.

9.1.2. Stopping Rules for Dose-limiting Toxicity During Dose Escalation

Cohorts in the dose escalation portion will be expanded up to 9 subjects in the case of 1 or 2 DLTs. More than two DLTs in a dose escalation expanded cohort (N=9) will exceed

the MTD. At the time a third DLT is observed in any dose level in any cohort, even if < 9 subjects are enrolled, enrollment in that dose level will be discontinued and a lower dose level or intermediate dose level in that Cohort will be explored. Any delayed DLTs will be evaluated on a case-by-case basis. The SSC will provide additional oversight and will be reviewing safety on an ongoing basis and may make adjustments to this criterion based on the data.

Subjects who are tolerating a study drug dose level that is being reviewed due to DLTs that occurred in other subjects will not be automatically precluded from continued dosing during this safety review and will be allowed to continue dosing for as long as it is tolerated unless the safety review mandates dose reduction. After safety analysis by the Investigators and Sponsor (with FDA and IRB notification), a decision will be made whether to resume enrollment and continue dosing at the current dose or initiate a new cohort of subjects at a lower INT230-6 dose.

9.2. Possible Toxicities

Based on the safety experience in the first 70 patients, the most common treatment associated adverse event is injection site pain. Other constitutional adverse events (nausea, vomiting, decreased appetite and anorexia) have also been reported.

Additional theoretical toxicities that could be affected by INT230-6, which may or may not be increased with the combination of immune activating agents, such as hematologic, cardiovascular, hepatic, musculoskeletal, and other systems, and may include the following:

- Allergic reaction/hypersensitivity: Fever, chills, shakes, itching, rash, hyper- or hypotension, and difficulty breathing. It is likely that most injection-related adverse events will occur within the first 24 hours after the injection and may be treated by supportive treatment as indicated.
- Injection procedure: Pain during and after the injection, bleeding, infection, tumor ulceration and edema. The needle utilized for this is the same or smaller size than what is typically used for a biopsy. All attempts at using a single injection point for each tumor are suggested. Additionally, injection volumes of liquid into the tumor should provide some back pressure to help reduce the potential for bleeding. The Quadrafuse device has been used for injection of deep tumors and has a low rate of hemorrhage as a complication.
- Other potential adverse effects of INT230-6: Fatigue, anemia, leukopenia, hyponatremia, other laboratory abnormalities (including increases in gamma-glutamyl transferase (GGT), aspartate aminotransferase (AST) and alanine aminotransferase (ALT), lipase, creatinine), nausea or vomiting, decreased appetite, weight loss, muscle aches, chills, dizziness, and urinary retention.
- Adverse effects associated with IV Cisplatin and Vinblastine are less likely given the dose used in this study: Renal damage, visual disturbances, hearing loss/tinitis, peripheral neuropathy, sensory loss/numbness, tingling, areflexia

and difficulty walking, xerostomia or xerosis, dehydration, dysgeusia, alopecia, thrombocytopenia, other blood abnormalities (low magnesium, calcium, potassium), bleeding, dark urine, chest pain or heart attack, sweating, depression, muscle cramps, pain including headaches.

- Extravasations: There are no reports of simultaneous extravasations of CIS and VBL so guidance on countermeasures does not exist. Also watch closely for any toxicities when given intradermally for skin tumors.

9.2.1. Management of select AEs

The following table describes potential AEs and the management suggestions for INT230-6. The investigator should use good medical judgement in determining the optimal care for his or her subjects.

Table 9: Dose Modification and Toxicity Management Guidelines for AEs Associated with INT230-6 using CTCAEv4.03

General instructions:

1. For situations where INT230-6 has been withheld, INT230-6 can be resumed after AE has been reduced to baseline or Grade 1
2. For severe and life-threatening AEs, INT230-6 should be permanently discontinued

AEs	Action taken to INT230-6	AE management	Monitor and follow-up
Allergic reaction or hypersensitivity	Hold drug if Grade ≥ 3	Follow the package insert for CIS and VBL, these AEs usually can be managed with by administration of epinephrine, corticosteroids, and antihistamines.	You may consider a rechallenge with INT230-6 if grade ≤ 2 and resolves with minimal treatment.
Typical cytotoxic effects including fatigue, nausea, vomiting, anorexia, decreased appetite	Hold drug if Grade ≥ 3	Supportive care as per institutional guidelines	Consider using anti-emetic premedication on next INT230-6 dose
Local reactions	Hold drug if Grade ≥ 3	apply heat packs, subcutaneous hyaluronidase	Consider prophylactic antihistamines and low dose corticosteroids on next INT230-6 dose
Injection pain	Hold drug if Grade ≥ 3	Pain control medications as prophylaxis and for treatment as per institutional standard	Consider prophylactic pain medication prior to subsequent injections. If Grade 3 or higher, do not increase INT230-6 dose

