13.1. Definitions

An adverse event is any undesirable sign, symptom, clinically significant laboratory abnormality, or medical condition occurring after starting study treatment, even if the event is not considered to be study drug-related. Each adverse event is to be reported on an Adverse Event CRF page. Adverse events are graded using the Cancer Therapy Evaluation Program (CTEP) CTCAE, Version 4.03. If CTCAE grading does not exist for an adverse event, the severity of mild (1), moderate (2), severe (3), life-threatening (4), and death related to an adverse event (5) will be used. Information about all adverse events, whether volunteered by the subject, discovered by Investigator questioning, or detected through physical examination, laboratory testing, or other means, will be collected, and recorded on the Adverse Event CRF page and followed as appropriate. Adverse event monitoring should be continued until adverse event resolution/stabilization (whichever is later).

Medical conditions/diseases present before the injection of study drug are only considered adverse events if they worsen after receiving any study drug. Clinical events occurring before the administration of study drug but after signing the ICF and providing HIPAA authorization are to be recorded on the Medical History/Current Medical Conditions CRF page. All laboratory values are to be reviewed by the Investigator and abnormal values will be graded according to CTCAE Version 4.03 and reported in the study report.

A laboratory abnormality is considered an adverse event if it results in:

- discontinuation from study drug,
- necessitates therapeutic medical intervention,
- if the Investigator assesses the abnormality as an adverse event, or
- any laboratory test that is clinically significant or meets the definition of a SAE

It is expected that wherever possible, the clinical, rather than the laboratory term would be used by the reporting investigator (e.g., anemia versus low hemoglobin value). These adverse events will be recorded on the Adverse Events CRF page and will include all signs, symptoms, or diagnosis associated with them.

As far as possible, each adverse event will also be described by:

1. Description
2. Duration (start and end dates)
3. CTCAE Grade 1 through 5 or severity if CTCAE is not available
4. Relationship to the study drug - related or not related
5. Relationship to the dosing procedure – related or not related
6. Action(s) taken with study drug

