Adverse events will be coded using the Medical Dictionary for Regulatory Activities (MedDRA) to categorize a system organ class and a preferred term for each adverse event. The number of subjects who experienced at least 1 adverse event, study drug related adverse event, severe (Grade 3 or above) adverse event, serious adverse event, and the number of subjects withdrawn due to adverse events will be summarized. For each system organ class and preferred term, summaries will be made with respect to the number and proportion of subjects having at least 1 occurrence of an adverse event during the study, using the worst grade reported within a subject. The incidence of adverse events will be presented overall, by system organ class and preferred term, intensity (based on NCI CTCAE Version 4.03), and additional grouping by severity and relationship to study drug. Individual listings of adverse events will be provided.

DLTs and study drug-related Grade >2 adverse events will be listed individually.

Physical Examination

Abnormal PE findings with onset prior to first dose of study drug will be recorded as medical history. Any abnormal or clinically significant findings on or after dosing will be recorded as an adverse event. Clinical significance will be determined by the Principal Investigator at each site.

Individual medical/surgical history will be listed by subject. Individual abnormal or clinically significant PE findings after dosing will be recorded as an adverse event and listed separately with AEs.

Vital Signs

Vital sign measurements and change from baseline will be summarized. Vital signs include weight, systolic blood pressure (SBP), diastolic blood pressure (DBP), body mass index (BMI, derived), heart rate, oxygen saturation, and temperature. Individual vital sign measurements will be listed.

ECGs

ECG data will be read and interpreted locally. Summary statistics of ECG overall interpretation will be displayed. Per subject ECG test results at will be listed.

Abnormal clinically significant ECG findings on or after informed consent will be recorded as an adverse event and displayed with AEs.

Clinical Laboratory Tests

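### Protocol Table 9 gives two opposite actions after a severe adverse event: stop INT230-6 permanently, or hold it with resumption allowed

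*Protocol*

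**What the plan says.** Protocol 9.2.1 introduces Table 9 as suggestions for managing adverse events, to be used with the investigator's judgement. The table grades by CTCAE v4.03 and opens with two general instructions:

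- Instruction 1: "For situations where INT230-6 has been withheld, INT230-6 can be resumed after AE has been reduced to baseline or Grade 1".
- Instruction 2: "For severe and life-threatening AEs, INT230-6 should be permanently discontinued".

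Four rows follow: allergic reaction or hypersensitivity, typical cytotoxic effects, local reactions, and injection pain. The action column is the same in each: "Hold drug if Grade ≥ 3". No row calls for discontinuation. Two follow-up cells bear on later dosing:

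- Injection pain: "If Grade 3 or higher, do not increase INT230-6 dose".
- Allergic reaction: "You may consider a rechallenge with INT230-6 if grade ≤ 2 and resolves with minimal treatment".

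Permanent discontinuation has its own section, 8.12, which begins "INT230-6 should be permanently discontinued for a subject due to the occurrence of any of the following AEs". That sentence goes on to limit the rule to events still unresolved when the next treatment is due.

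**The concern.** A site that sees a Grade 3 event named in Table 9 finds one line telling it to end INT230-6 for that subject and another telling it to pause and, on recovery, permitting it to restart. These are opposite actions, and the table does not say which line governs.

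The events concerned are central to the trial. The primary objective is assessed by the rate of Grade 3 or higher events attributed to treatment (protocol 4.2), and injection site pain is the most common treatment-associated event (protocol 9.2). If sites resolve the conflict differently, subjects with the same event are handled differently. Their later exposure then differs, as do the counts of subjects who stop because of an adverse event.

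**Working it through.** There is no figure to recompute; the check compares texts.

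**Step 1: what grade is severe?** Protocol 14.3.5 summarises subjects with a "severe (Grade 3 or above) adverse event", and SAP 10.1 glosses severe in the same way. With that meaning, instruction 2 starts at Grade 3.

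**Step 2: what does each row of Table 9 give at Grade 3 or higher?**

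| Row | Instruction 2 | Row action | Later dosing after Grade 3 or higher |
|---|---|---|---|
| Cytotoxic effects | Stop permanently | Hold | Open under instruction 1; follow-up cell refers to premedication for the next dose |
| Local reactions | Stop permanently | Hold | Open under instruction 1; follow-up cell refers to prophylaxis for the next dose |
| Injection pain | Stop permanently | Hold | Open under instruction 1; follow-up cell limits the dose after such an event, so it presupposes a further dose |
| Allergic reaction | Stop permanently | Hold | Instruction 1 only; the row ties rechallenge to Grade 2 or lower |

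Three rows conflict clearly with instruction 2. The allergic row conflicts less clearly, because its own follow-up cell is narrower than instruction 1 and because 8.12 separately lists anaphylactic-type reactions.

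**Step 3: does a narrower reading of instruction 2 remove the conflict?** Suppose severe and life-threatening are read together as Grade 4 only. Grade 3 then has one action, hold. At Grade 4 the conflict remains, because neither the rows' hold trigger nor instruction 1 has an upper limit.

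**Step 4: do other sections decide the matter?**

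- *8.12* requires discontinuation for listed events that are unresolved before the next treatment, plus any event the investigator judges a substantial clinical risk. Severe nausea or vomiting, for example, leads to discontinuation only if it persists despite maximal supportive care. The listed thresholds are not uniformly Grade 3: neuropathy enters at Grade 4. None of this equals stopping for every severe event.
- *5.5* bars repeat injection only where an attributable event above Grade 2 persists.
- *9.1.1* sends related Grade 3 or higher events after cycle 1 to the Study Steering Committee, to consider changes in that subject's dose level or frequency. It does not provide for automatic discontinuation.

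None of the three matches instruction 2, and none says that it overrides Table 9 or yields to it.

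**Step 5: which analyses are touched?** Under either action, the event that triggers the decision is already counted in the Grade 3 or higher rate. What can differ is what follows: further doses and the chance of further events, the reasons for premature discontinuation (SAP 8.1), and withdrawals or discontinuations due to adverse events (protocol 14.3.5, SAP 10.1). Cumulative dose is also the numerator of the percentage of tumor burden dosed (SAP Appendix 1, item 2), which defines the groups below 40% and at or above 40% in the survival curves (SAP 9.2).

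**The case against.** The best defence has four parts.

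*The table is advisory.* It is introduced as suggestions and leaves room for clinical judgement. This softens the conflict. It does not tell a site which of two opposite written actions the protocol intends.

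*Holding can be a first step.* The rows and 8.12 can be read together: hold, then stop if the event has not resolved. That reading is coherent, but it leaves no role for instruction 2 in events that do resolve. Being the odd one out does not show that instruction 2 is the error.

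*The definition of severe comes from analysis text.* Protocol 14.3.5 and SAP 10.1 label summary tables; they do not set dosing rules. This is fair, and it is why the Grade 4 reading was also tested. A reader might instead rely on the severity scale in protocol 13.1. That scale applies only where no CTCAE grading exists, so it does not by itself govern a table graded by CTCAE.

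*Oversight limits variation.* The Steering Committee reviews later Grade 3 events. The Medical Monitor must approve dose reductions (8.9) and continuation after a delay of more than two weeks (8.11). These controls narrow the differences between sites but do not choose between the two instructions.

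**Conclusion.** Table 9 contradicts itself. With severe taken as Grade 3 or above, three of the four rows conflict clearly with instruction 2 and the allergic row conflicts less clearly. With instruction 2 confined to Grade 4, the conflict is confined to Grade 4. Sections 5.5, 8.12 and 9.1.1 do not resolve it.

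The size cannot be computed: the documents do not say how many subjects had such an event or how sites handled it. The rationale for Amendment 5 describes side effects as mainly low-grade injection-site pain, which suggests that few pain events reached this threshold. The texts of Supplement Tables 22 and 28, whose titles are similar, were not available, so this conclusion covers the main protocol only.

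Two stronger inferences are not supported:

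- A reader might infer that the primary endpoint is miscounted. The triggering event counts under either action; only later exposure and later events could change.
- A reader might infer that 8.12 excludes Grade 3 injection pain and local reactions. It does not name them, but its investigator-judgement clause can reach them.

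What remains is a safety-relevant inconsistency that is cheap to correct and should be corrected.

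**What to change.** Reconcile Table 9's two general instructions and four rows with sections 8.12, 5.5 and 9.1.1, so that each event type and grade has one stated action and the governing section is clear. Check Supplement Tables 22 and 28 for the same wording. Which action applies is a clinical decision for the sponsor and the Steering Committee; this review does not propose one.

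The cost is a clarification letter or a short amendment. The SAP reports final enrollment of 110 subjects and describes edits in preparation for study closure, so few subjects may still be on treatment. If dosing has ended, the study report should instead state which rule sites applied after Grade 3 or higher events. The action taken with study drug is already recorded for each adverse event (protocol 13.1) and listed (SAP 10.1), so this needs no new data collection.
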